3.2 Baseline Assessment

At 2 weeks post-surgery, patients will attend orthopaedics and physiotherapy outpatient clinics to assess wound and fracture healing (**Error! Reference source not found.**).

Wound will be reviewed by the orthopaedic department/nurse. If wound healing is satisfactory, a tubular compression bandage will be applied. The Aircast boot will be reapplied.

Patients will be instructed on inflation of the Aircast boot, and will be provided a link to this video for future reference: <https://www.youtube.com/watch?v=XnBm68oTD0w>.

Patients will be instructed that the inflation of the Aircast boot may need to be adjusted as swelling reduces.

Patients will be given instructions, by the physiotherapist, about how partial weight-bearing, which can begin following the first follow-up visit. Additionally, their exercise protocol will be reviewed, and patients will be advised on an exercise regime. They will also be instructed in the charging of the battery of the Magnes device.

Measurements will be taken according to the schedule described in Table 2.

The Magnes device data will be downloaded for the first time since surgery, allowing for an evaluation of foot use and weightbearing activities since surgery.

3.2.1 Assessment 2

At 5-6 weeks post-surgery, patients will attend the orthopaedics and physiotherapy outpatient clinic for their second follow-up visit (**Error! Reference source not found.**).

At this visit and depending on the stage of healing of the fracture, the Aircast boot will be substituted by the Magnes NUSHU.

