2.8 Study Intervention

Current practice in the orthopaedic clinics of the RWBH includes fitting all patients operated for an ankle fracture with an Aircast AirSelect Standard walker boot (**Figure 1A**) in the operating theatre. As such, patients will be screened and consented in the pre-operative phase.

The Aircast Airselect Standard walking boot (hereafter referred to as the Aircast boot or Aircast) is shown in Fig. 1A. The Aircast is considered part of standard care for these ankle fracture patients. In clinical practice, the Aircast boot is utilised for fractures of the foot, ankle and distal tibia or fibula, high-grade ankle sprains and for postoperative immobilisation. It offers several advantages over traditional casts such as allowing easier access to the surgical wound, the ability to adjust the Aircast boot depending on swelling and improved durability when used as a walking device.

Those patients who consent to participate in the study will be fitted with the Aircast boot as per usual practice with the addition of a Magnes device attached to the boot, as shown in **Figure 1A**, in the operating theatre following surgical fixation.

[figure not shown]

Figure 1: *The Aircast boot with the Magnes smart device (1A) and the Magnes NUSHU (1B) It has anterior and posterior semi-rigid outer shells that when tightened, using the three straps, immobilises and supports the ankle and provides protection. An inner lining protects the limb from skin irritation. The Aircast has two adjustable distal air cells within the shell that inflate to support the malleoli and provide compression to decrease swelling. The Aircast is available in sizes XS – XL, allowing a suitable fit for most patients.*

In addition, patients will receive a standard information and education leaflet designed for the study (Appendix 1). The information and education leaflet includes information about the smart devices and their care (smart device in the Aircast and the NUSHU shoe) and information on postoperative care (practical guide, weight-bearing, other activities and exercises). This leaflet will facilitate standardisation of the postoperative rehabilitation across patients. (Appendix 1).

Post-operatively patients will be offered up to 6 physiotherapy sessions in fortnightly intervals as per usual practice. (Appendix 2).

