APPENDIX 1: Rehabilitation protocol

Ankle Fracture - Post operative Physiotherapy

The following is a guide only, please check for any changes or variances as indicated by your surgeon's post-operative plan.

(Excludes tibial plafond fractures and large posterior malleolar fractures)

0 to 2 weeks Gentle walking and elevation PWB

- Physiotherapy review post operatively for crutches
- Apply air-cast boot in theatre after surgery – No inflation
- **PWB (partial weight bear)** in air-cast boot with crutches is ok
You may opt to NWB (non-weight bear) due to pain, this is ok too.
After 3-5 days start to try and take some weight (<50% of your weight) on your

foot with the boot

- Keep boot on at all times - leave on 24/7 but check your skin underneath by undoing daily to view your skin by removing the front panel
- Rest and elevate to allow for wound healing – aim to keep your leg elevated 23hrs/day
 - When sitting elevate your leg on a foot stool, chair or up on sofa
 - When lying down, you can elevate your leg on a single pillow
 - Don't walk too much, aim for essential walking within your home in the first week
- Do not get dressings wet – cover your lower leg in a cast bag for showering
- Leave dressings intact for 10-14 days - until the '2 week' follow up
- Around 2 weeks you will have dressing removed and wound reviewed by a doctor
- A tubi-grip will be applied and the air-cast boot re-applied
- Teach application of air-cast boot – **but not to inflate for first 2weeks** and until dressing removed

Video demo: <https://www.youtube.com/watch?v=XnBm68oTDOw>

Crutches PWB = Partial Weight Bear

= <50% of your body weight

Boot on at all times

- Aim for ankle in neutral (90°)
- Can be refitted if needed to ensure heel down
- Or to check skin condition daily.

[figure not shown]
Walking with crutches:

- Crutches in front first, boot foot next taking **Partial weight** as pain allows (**up to 50% of your body weight**), good foot follows stepping up to (not past) operated foot (can use scales to check weight you're

2 to 6 weeks Progress more weight onto foot and start ankle movement WBAT

WBAT (weight bear as tolerated = up to full weight) in air-cast boot with crutches, boot inflated

- Boot on for all walking using 2 crutches
- You may be able to manage with 1 crutch indoors (crutch in opposite hand to foot)
- If painful or limping continue with 2 crutches
- Aim for step-through gait – Physiotherapist to review and advise

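### Section 3.2 starts partial weight-bearing after the 2-week visit, contradicting the Appendix 1 leaflet that patients follow from surgery (minor; correct section 3.2)

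*Protocol*

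**What the plan says.** Section 3.2 of the protocol describes the baseline visit at 2 weeks. The physiotherapist then gives instructions "about how partial weight-bearing, which can begin following the first follow-up visit". Section 2.9 places the first orthopaedic follow-up at about 2 weeks, so the in-hospital physiotherapy review cannot be the visit meant.

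The Appendix 1 leaflet labels weeks 0 to 2 as partial weight-bearing. It says that this "in air-cast boot with crutches is ok", and it continues: "After 3-5 days start to try and take some weight (<50% of your weight) on your" foot in the boot. It also leaves an exit: "You may opt to NWB (non-weight bear) due to pain, this is ok too". For weeks 2 to 6 the instruction becomes "WBAT (weight bear as tolerated = up to full weight) in air-cast boot with crutches, boot inflated".

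On the leaflet's standing, section 2.8 says: "This leaflet will facilitate standardisation of the postoperative rehabilitation across patients". Appendix 2 says that advice on rehabilitation and the boot follows Appendix 1. The leaflet itself opens: "The following is a guide only, please check for any changes or variances as indicated by your" surgeon's postoperative plan.

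Section 3.1 lists two feasibility outcomes for Aim 1, which covers week 1 to about week 6. One is the correlation of instructed with actual weight-bearing, in intensity and in total time.

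**The concern.** Two operative parts of the protocol use the same term, partial weight-bearing, with different start dates. A physiotherapist working from section 3.2 and a patient working from the leaflet could act on different advice in the first two weeks after fixation, when early loading matters clinically.

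The same sentence bears on a named outcome. The correlation needs an instructed load as its reference, and section 3.2 plans to evaluate weight-bearing from surgery onward at the first download, so these weeks are in the data. A patient who loads the boot at 40% of body weight on day 7 follows the leaflet but appears to depart from section 3.2.

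**Working it through.** The protocol gives no figure to reproduce, so the check is a comparison of passages followed by a count of the days affected.

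**Passages side by side**

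| Period | Section 3.2 | Appendix 1 leaflet | Compatible? |
|---|---|---|---|
| Surgery to day 3-5 | Partial weight-bearing not yet begun (inferred) | Partial allowed; none accepted if painful | No |
| Day 3-5 to 2-week visit | Not yet begun (inferred) | Start taking some weight, <50% of body weight; none accepted if painful | No |
| After the 2-week visit | Partial can begin | As tolerated, up to full weight | Yes: partial loading lies within as tolerated |

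**Which passage governs.** Appendix 2 points to Appendix 1 as the source of the advice. Four other places fit early loading, although none states a load:
- Section 2.9: a physiotherapist teaches the rehabilitation plan before discharge.
- Section 2.7.2: trimalleolar fractures unsuited to early weight-bearing are excluded.
- Section 3.2: weight-bearing since the operation is evaluated at the first download.
- Appendix 2: the first two weeks are described as gentle walking.

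Section 3.2 is therefore the outlier.

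**Calendar share.** Inputs: about 6 weeks in the boot (section 3.1, Aim 1), first visit at about 2 weeks (section 2.9), 12 patients (section 2.4).
- Boot period: 6 × 7 = 42 days per patient; 12 × 42 = 504 patient-days.
- Surgery to the 2-week visit: 14/42 = 33%; 12 × 14 = 168 patient-days.
- From the leaflet's active prompt only: (14 − 5)/42 = 9/42 = 21% to (14 − 3)/42 = 11/42 = 26%; 12 × 9 = 108 to 12 × 11 = 132 patient-days.

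These are shares of time, not of loading and not of any effect on the correlation. The document gives nothing from which that effect could be computed.

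**Is the individual instruction recorded?** The weight-bearing row of Table 1 (section 4.0) lists sensor data only. The REDCap forms in Appendix 5 show no field for instructed load. Those forms also lack other Table 1 items, such as return to work, so the missing field is weak evidence by itself. Clinical notes may hold the instruction, but no passage says that they will be used.

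**The case against.** The strongest reply is that the leaflet plainly governs. Every patient receives it, Appendix 2 names it as the source of advice, and the section 3.2 sentence is visibly garbled and only describes what is said at 2 weeks. Nobody is described as telling patients to bear no weight before then. On this view the conflict is a stray clause in a 12-patient single-group study with no decision threshold attached, and the sourcing of the instructed load belongs in the analysis plan.

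Most of this stands. It settles which passage is wrong and keeps the point minor. It does not remove the contradiction: the timing clause is clear even though the sentence is not, and staff will read it. A later analysis plan can choose a reference value, but it cannot recover an individual instruction that was never collected.

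A reader might infer more than the documents support:
- **That the instructed load for weeks 0-2 is undetermined, or nil.** Nil is only an inference from section 3.2, and Appendix 2 identifies the leaflet as the source.
- **That one third of the correlation is compromised.** The 33% is calendar time. Loading in those weeks is meant to be light.
- **That the leaflet fixes a reference time of 1 hour a day**, from "aim to keep your leg elevated 23hrs/day". That is an aim, and a leg that is not elevated is not necessarily bearing weight.
- **That the schedules also conflict in weeks 2-6.** Partial loading is contained in weight-bearing as tolerated, so this is a difference of wording only.

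**Conclusion.** The contradiction is real and lies in section 3.2. It concerns the first two of about six Aim 1 weeks. The risk is that early loading is advised or scored against the wrong start date, with an effect on the correlation that cannot be computed. Severity is minor. The conclusion assumes that the first follow-up visit in section 3.2 is the one that section 2.9 places at about 2 weeks, and that the clinical leads confirm the leaflet as the intended schedule.

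Even with section 3.2 corrected, the leaflet gives a ceiling with an opt-out, and the surgeon may vary it. It can serve as the default reference, but the instruction given to a particular patient may differ. That is the reason to record it.

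**What to change.** Subject to confirmation by the clinical leads:

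1. Replace the clause in section 3.2 with: *Partial weight-bearing (<50% of body weight) in the uninflated boot with crutches is permitted from surgery and encouraged after 3-5 days, with non-weight-bearing acceptable if painful; from the 2-week visit patients may bear weight as tolerated in the inflated boot.* This keeps the day 3-5 prompt and the opt-out for pain, and it aligns the week-2 wording.
2. Add one sentence to section 3.1 naming Appendix 1 as the default source of the instructed load.
3. Record each patient's instructed load (a percentage limit, or as tolerated) at the pre-discharge physiotherapy review and at the existing physiotherapy sessions, and use it in the correlation. No walking-time field is needed.

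The cost is two sentences and one extra data field completed at contacts already planned, with no additional patients or visits. The small downside is the extra field to complete.

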3.2.2 Final appointment

At 12 weeks post-surgery, patients will attend the orthopaedics and physiotherapy outpatient clinic for their third and final follow-up visit (**Error! Reference source not found.**) after which they will be discharged.

Outcome measures such as range of movement, AFORM and EQ-5D 5L questionnaires as well as downloading the data from the sensor will occur during these two follow-up visits.

4.0 Data collection

Data will be collected at 2 weeks post-surgery (baseline for this study), and at 6- and 12-weeks follow-up. Non identifiable baseline data, such as gender and age, will be recorded, in addition to non-identifiable health related data, for example, date of injury, injury cause, imaging reports and type of surgery. This information will be recorded on a secure, password protected Metro North REDCap server. See Appendix 5 for a pdf of the REDCap data dictionary. Range of movement, AFORM and EQ-5D 5L: measures will be taken at each follow-up visit.

Table 1: Outcomes to be recorded at patient follow-up visits

No.	Measurement	Description	When measured
Ability to use technology: insoles and iPad App			
1.	Data upload	Has the data been uploaded to the cloud successfully for the time period in question	2, 6, 8, 10 and 12 weeks
2.	Device charging and monitoring	How long each day did the patient wear the boot/shoe? Did the device remain charged (and able to record data) for the time period in question? Were there any problems related to keeping the battery charged?	2 weeks, 6 weeks, 12 weeks
3.	Other issues raised by the patient	Description of any other problems faced by the patient that limit their ability to use the device and capture data.	2 weeks, 6 weeks, 12 weeks
4.	Ownership of a smartphone	Patients will be asked if they own a smartphone (necessary as the future randomised trial will require this)	At recruitment
Patient Reported Outcome Measures			
5.	AFORM	Standardised questionnaire, filled in by the patient.	2, 6 and 12 weeks
6.	EQ-5D 5L: EuroQol five-dimension health utility tool	Standardised questionnaire, filled in by the patient.	2, 6 and 12 weeks
7.	Return to work	Has the patient returned to work? Is the patient able to return to work?	2, 6 and 12 weeks
8.	Medication review	Consumption of OTC and prescription analgesics	Daily for 12 weeks
Other clinical measures			
9.	X-ray ankle	XR ankle: WB out of cast – AP/lateral/mortise	6 weeks
10.	Wound review	Orthopaedic Department Nurse	2 weeks
11.	Weight-bearing	Magnes Sensor Data	2-6 -8*-12 weeks

No.	Measurement	Description	When measured
12.	Complications	Orthopaedic Department Nurse	Throughout the duration of the project
Range of Motion Measures			
13.	Ankle dorsiflexion (DF)	Measured using a standard goniometer	2, 6 and 12 weeks
14.	Ankle dorsiflexion (DF) (knee to wall)	Measured using a standard ruler	2, 6 and 12 weeks
15.	Ankle plantarflexion (PF)	Measured using a standard goniometer	2, 6 weeks, 12 weeks
16.	Ankle plantarflexion (PF) (knee to wall)	Measured using a standard ruler	2, 6 and 12 weeks
17.	Ankle range of motion (ROM)	Measured using a standard goniometer	2, 6 and 12 weeks

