Physiotherapists, orthopaedic surgeons and researchers at the RBWH and the Jamieson Trauma Institute (JTI) have recognised these problems and see the potential to improve the care of patients following surgery for ankle fractures, by streamlining and improving rehabilitation using digital innovations, such as smart orthotics to record weight-bearing, and smartphone apps to record pain scores, adherence to rehabilitation programmes and medication use. A number of these devices have been developed in recent years. For the purposes of this study the Magnes device (Magnes AG, Switzerland) will be used.

Studies to date evidence the important of early weight-bearing and mobilisation(2, 3) but identifying the optimal amount of weight-bearing exercise at different stages of rehabilitation is a recurring challenge in the rehabilitation of patients with ankle fractures (4). At present, clinicians do not have good evidence upon which to base their guidance about when to begin partial or full weight-bearing on their injured leg or other aspects of their rehabilitation protocols (3). As such, the best weight-bearing protocol following ankle fracture surgery, for optimal recovery, is currently unknown.

A further key challenge is that, currently, clinicians are able to monitor patient progress only during face to face or telehealth appointments, therefore gathering evidence of adherence with rehabilitation programs is based on patient recall of activities between appointments.

These challenges are consistent with the preliminary results of our systematic review (in progress) of postoperative rehabilitation of patients with ankle fractures, which shows a lack of evidence to guide decisions about rehabilitation intensity and timing of weight-bearing for optimal fracture healing and functional recovery.

Advances in technology present new opportunities for addressing these issues through remotely tracking patient progress and allowing the clinician to identify the optimal amount of weight-bearing exercise at different stages of rehabilitation, thus reducing reliance on patient recall. In the context of ankle fractures, smart devices may allow real-time gait data capture and in-depth analysis of weight-bearing throughout recovery.

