6.0 Risks and Benefits

This study is not changing any aspect of standard clinical practice in the treatment and rehabilitation of ankle fractures so there is no additional risk from participating. The only additional burden is that the participant will complete two questionnaires at three timepoints and they will be required to charge the Magnes device once a day. There will be no direct benefit to individuals as a result of participating in this study. However, they will indirectly contribute to advances in ankle fracture rehabilitation practices, and in streamlining aftercare in this population. Participants will not be reimbursed for their time.

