APPENDIX 2: Rehabilitation timeline

Rehabilitation strategy

Patients will be followed up at 2, 6 and 12 weeks after their surgery (as per standard clinical care), at physiotherapy and orthopaedics department outpatient clinics at the Royal Brisbane and Women's Hospital (Brisbane, Queensland, Australia) (**Error! Reference source not found.**). Physiotherapy appointments will occur in fortnightly intervals from week 2 post-operatively. In total, patients will receive 6 sessions of physiotherapy treatment. Outcome measures will be recorded on the 1st, 3rd and 6th attendance of the patient for their physiotherapy and orthopaedic follow-up appointments (wks 2, 6 and 12 post-operatively).

[figure not shown]

Figure 2. The patient's postoperative timeline, including assessment time points.

The rehabilitation exercises that patients will be instructed to do are described in APPENDIX 2. The information booklet provided to patients will include instruction sheets with cartoons showing how to perform each of the exercises (Appendix 1). Patients will be advised as to their rehabilitation, pain relief and the Aircast boot according to the information in (Appendix 1). The wound dressings will be left intact until the first follow-up visit, 10 to 18 days after surgery.

Surgery date to 2 weeks post-surgery: Gentle walking and Elevation (**Error! Reference source not found.**)

[figure not shown]

Figure 3. The patient's postoperative timeline from surgery to assessment 1.

Aircast boot

The Aircast boot should remain on at all times and **should not be inflated during the first two weeks of the postoperative period**. During showering/bathing, the cast should be covered using a plastic bag, to ensure the boot and wound dressings do not get wet.

Charlson Comorbidity Index

Chart review version

Components of classical Charlson Comorbidity Index¹

1. Has the patient had a myocardial infarction? (MI)

- No
 Yes

Criteria: Myocardial infarction includes patients with one or more definite or probable myocardial infarction. These patients should have been hospitalized for chest pain or an equivalent clinical event and have had electrocardiographic and/ or enzyme changes. Patients with electrocardiographic changes alone who have no clinical history are not designated as having had an infarction.

2. Has the patient been hospitalized or treated for heart failure? (CHF)

- No
 Yes

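### Device wear, charging and problem items look back up to 42 days although patients attend every 14 days, and the daily analgesic record has no stated collection route

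*Protocol*

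**What the plan says.** **Rows 2 and 3 of Table 1 (section 4.0).** Row 2 asks "How long each day did the patient wear the boot/shoe", whether the device stayed charged and able to record, and "Were there any problems related to keeping the battery charged? 2 weeks, 6 weeks, 12 weeks". Row 3 asks for any other problems that the patient met in using the device, on the same three dates. Appendix 2 agrees: outcomes are recorded at the first, third and sixth attendance.

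**Attendance.** Appendix 2 states "Physiotherapy appointments will occur in fortnightly intervals from week 2 post-operatively", six sessions in total. Sections 2.10 and 3.1 have the sensor downloaded at each of these fortnightly sessions.

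**What the answers feed.** Section 3.1 lists keeping the device charged as an acceptability outcome under both Aim 1 (boot) and Aim 2 (shoe). The synopsis gives feasibility of patient use of the device as the primary objective.

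**Recall.** Section 1 names as a weakness of present practice that "gathering evidence of adherence with rehabilitation programs is based on patient recall of activities between appointments", and offers remote tracking as a way to depend on it less.

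**Row 8 and burden.** Row 8 reads "Consumption of OTC and prescription analgesics Daily for 12 weeks". Section 6.0 says "The only additional burden is that the participant will complete two questionnaires at three timepoints", plus daily charging of the device.

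**The concern.** Row 2 asks for a daily quantity but is answered three times in 12 weeks. By week 12 the question reaches back six weeks, and three physiotherapy sessions at which it could have been asked (weeks 4, 8 and 10) have passed without it. A patient who is asked at week 12 about wear and charging in week 7 can give little more than a general impression.

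The week-12 question also covers a period when both devices may be in use. Section 2.8 moves patients to the shoe at about six weeks, while the Appendix 1 leaflet keeps the boot for outdoor use until week 8. Row 2 has one combined boot-or-shoe item, but Aims 1 and 2 evaluate the two devices separately.

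At stake is how well the study can report whether patients wore the devices, kept them charged and met problems. Those answers bear directly on its primary objective and on the planning of the later randomised trial.

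Row 8 raises a different question. It calls for a daily record in a table headed as outcomes taken at follow-up visits, and the protocol does not say how the daily entries are made.

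**Working it through.** **Inputs (all from the protocol).** Rows 2 and 3: weeks 2, 6 and 12 (Table 1). Physiotherapy: fortnightly from week 2, six sessions (Appendix 2). Follow-up: surgery at week 0 to week 12, 12 × 7 = 84 days. Target sample: 12 patients (section 2.4).

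**Reproducing the plan's own figure.** Fortnightly from week 2 to week 12 gives weeks 2, 4, 6, 8, 10 and 12, which is six sessions. The first, third and sixth fall at weeks 2, 6 and 12, as Appendix 2 states.

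**Look-back under the present schedule.** Look-back = (this week − previous week) × 7.

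| Asked at week | Look-back | Days older than 14 days when asked |
|---|---|---|
| 2 | (2 − 0) × 7 = 14 | 14 − 14 = 0 |
| 6 | (6 − 2) × 7 = 28 | 28 − 14 = 14 |
| 12 | (12 − 6) × 7 = 42 | 42 − 14 = 28 |
| Total | 84 | 42 |

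Share recalled more than 14 days later: 42 / 84 = 50%.

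**Sensitivity to visit timing.** Section 3.2.1 places the second assessment at 5 to 6 weeks. At week 5 the look-backs are 14, 21 and 49 days, and the days beyond 14 are 0 + 7 + 35 = 42. The 50% is unchanged and the longest look-back grows to 49 days.

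**Look-back if rows 2 and 3 are taken at all six sessions.** 6 × 14 = 84 days, longest look-back 14 days, no day beyond it. Records per patient rise from 3 to 6, or from 36 to 72 over 12 patients. This assumes full attendance: if week 10 is missed, the week-12 look-back is 28 days.

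**Who supplies the answer.** The protocol does not say for row 2, so the items have to be taken one by one.

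- Other problems (row 3): from the patient, by the row's own title.
- Problems in keeping the battery charged: in practice from the patient.
- Wear time: probably from the patient. Section 3.1 lists gait and loading outputs for the device, and wear time is not among them. A charge lasts about 16 hours, while Appendix 1 has the boot on day and night in the first two weeks with the leg mostly elevated. The protocol does not say that a worn but unloaded boot can be told from a removed boot or a flat battery.
- Charge and recording status: possibly readable from the download, though the protocol does not say so.

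**Row 8.** As scheduled, the interval is one day: 84 entries per patient, 84 × 12 = 1,008 in all. No diary or other tool is named. The REDCap forms in Appendix 5 have no field for analgesic use, and none for wear time or charging. Section 6.0 counts two questionnaires and charging, but neither the daily record nor the telephone interview in section 3.1.

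**The case against.** The strongest reply is that row 2 need not be patient-reported at all. Neighbouring rows name the patient as source and row 2 does not; it sits outside the patient-reported block, and section 3.2 uses the download to evaluate foot use since surgery. This stands for charge and recording status, so the 50% figure must be conditional. It does not reach row 3 or the battery-problem item, and it is weak for wear time, which is not a listed device output.

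A reader might infer that device use as a whole is measured by long recall. The documents do not support that: weight-bearing and gait come from the sensor, downloaded every two weeks. The recall criticised in section 1 concerns adherence to rehabilitation programmes, which is a related matter but not the same one.

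A reader might also infer that analgesic use is recalled over up to 42 days. Row 8 sets a daily schedule, and an incomplete burden statement does not cancel it. Section 1 mentions smartphone apps that record medication use, which could suggest a route. The protocol assigns no such app here, and row 4 asks about smartphone ownership only because the later trial will need it. What remains for row 8 is a missing collection route, not a long look-back.

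Finally, row 3 asks for a description and not for daily values, device-related adverse events and complications are recorded elsewhere, and attendance may be incomplete: section 2.8 offers up to six sessions, and section 3.1 provides for missed visits. These points reduce the size of the problem. They do not favour asking at three visits over asking at six.

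**Conclusion.** The point holds as a cheap improvement to a stated schedule. Rows 2 and 3 look back 14, 28 and 42 days where 14 days throughout is available at visits already planned. If patients supply the answers and attend as scheduled, 42 of 84 days (50%) are recalled more than 14 days later. The share falls for any item that is read from the device log. The effect is on the charge-keeping outcome of Aims 1 and 2, the reported wear time and the account of device problems. The merging of boot and shoe in the week-12 answer adds to it.

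The documents give no basis for the direction of any recall error, so no claim is made that it would favour the device. Nor do they support the view that every sensor value depends on wear time; peak load and step time, for example, do not.

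On row 8 the conclusion is narrower: a daily record is scheduled without a stated means of collection, and section 6.0 does not count it.

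**What to change.** 1. In Table 1, set rows 2 and 3 to weeks 2, 4, 6, 8, 10 and 12, taken when the sensor is downloaded. Row 1 lists uploads at weeks 2, 6, 8, 10 and 12; align it with the fortnightly download in sections 2.10 and 3.1, since the week-4 collection relies on it.
2. State the source of each row 2 item. Take charge and recording status from the download where the device log allows it, and keep patient questions for wear time and problems.
3. Record boot and shoe separately, so that weeks 6 to 8 can be assigned to Aim 1 or Aim 2.
4. Name the tool for the daily analgesic record in row 8 and reconcile it with section 6.0, which should also mention the interview. Do not replace the daily record by a seven-day question at the six visits: that would cover 6 × 7 = 42 of 84 days and lose half the period.
5. Add the matching fields to the REDCap forms in Appendix 5.

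The cost is a few extra minutes at visits already scheduled, plus edits to Table 1, section 6.0 and the data dictionary. No visit is added and care does not change.
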